6.2.7 Additional Data Collected

Additional data recorded on the CRF will include the subject's gestational age, days of life, weight, length, reason for admission, and skin tone. The skin tone will be evaluated using the Munsell System Soil Color Chart, Hue 7.5YR. The value score that best matched the subject's skin on the dorsal surface of the distal extremities was recorded.

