8 STATISTICAL CONSIDERATIONS

8.1 Sample Size Determination

Data from a study assessing the accuracy of both pulse oximeters on an adult population (Study ID # 2018-268) were used as parameters for sample size estimation for this protocol. Sample size estimation was conducted separately for each product using both the Confidence Intervals for One Standard Deviation Using Standard Deviation (as an estimate for the accuracy root mean square A_{RMS} statistic in equation 1.1 below) and Bland-Altman procedures in PASS 2020 Power Analysis and Sample Size Software (2020). NCSS, LLC. Kaysville, Utah, USA, ncss.com/software/pass. The most conservative estimate between the two products for the A_{RMS} sample size (18) and the Bland-Altman statistic (40) was used as the minimum number of data pairs, n. A data pair will consist of a pulse oximeter sensor reading paired with an ABG reading collected by a CO-oximeter. We selected a sample size of at least 80 total data pairs for each of the two product sensors, consisting of at least 40 data pairs per site per product sensor. We doubled this estimate and selected a sample size of at least 80 total data pairs per product sensor, such that no subject contributes more than three data pairs for each of the two product sensors, for a minimum of 27 subjects. The same blood gas value can be used for multiple sensors applied simultaneously.

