8.3. Populations for Analysis

All data pairs will be included for analysis, unless at the time of data acquisition any one or more of the following is true: (1) the SpO2 value is >100%; OR (2) the SpO2 value is \leq 0%; OR (3) the heart rate measurement derived from the pulse oximeter is 0 beats per minute; OR (4) the research personnel collecting the data notes an anomaly in the measurement on the CRF at the time of data collection before data analysis begins. Any such designated outliers and/or anomalous data will be explained and any data that is excluded from the analysis will be justified in the final report.

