8.4 Data Analysis

Accuracy of each pulse oximeter will be assessed per ISO 80601-2-61:2017, the FDA "Pulse Oximeters - Premarket Notification Submissions [510(k)s] Guidance for Industry and Food and Drug Administration Staff" document issued on March 4, 2013, and paper by Bland et al., 2007.^{3,4,5}

For each pulse oximeter, an accuracy root mean square (A_{RMS} , in equation 1.1 below) will be calculated to define the SpO₂ accuracy compared to the SaO₂ as measured by co-oximeter, as outlined in ISO 80601-2-61:2017 sub clause 201.12.1.101. It is expected that each of the sensors should achieve an $A_{RMS} \leq 3\%$ as per the testing of these same products in the protocol on adult subjects. In addition, mean Bias (B, in equation 1.2) defined per ISO 80601-2-61:2017 as the mean difference between the test and reference values, preserving sign, and precision (SD_{res} , in equation 1.3), defined per ISO 80601-2-61:2017 as the standard deviation of the residuals.

In the following equations, let

- SpO_{2_i} be the oxygen saturation value for the i^{th} data pair in the range of interest measured using the pulse oximeter
- SaO_{2i} be the reference oxygen saturation value for the *i*th data pair in the range of interest measured using the co-oximeter
- and *n* be the number of data pairs in the sample in the range of interest.

Then, per ISO 80601-2-61:2017 A_{RMS} is defined as:

$$A_{RMS} = \sqrt{\frac{\sum_{i=1}^{n} (SpO_{2_i} - SaO_{2_i})^2}{n}}$$
(1.1)

Mean bias B is defined as:

$$B = \frac{\sum_{i=1}^{n} (SpO_{2_i} - SaO_{2_i})}{n}$$
(1.2)

And precision (SD_{res}) is defined as:

$$SD_{res} = \sqrt{\frac{\sum_{i=1}^{n} (SpO_{2_i} - SpO_{2fit_i})^2}{n-2}}$$
(1.3)

where SpO_{2fit_i} is the difference between the *i*th datum and the value of the fitted curve corresponding to the *i*th reference value

For each pulse oximeter, a Bland-Altman plot (mean vs. difference of SaO_2 and SpO_2) and an error plot (SaO_2 vs. difference of SaO_2 and SpO_2) will be generated. Between and within subject variance and upper and lower 95% limits of agreement will be presented. Subject demographic data will be presented with summary statistics and site-level effects will be assessed as appropriate. Outliers will be explained and any data that is excluded from the data analysis or any deviations from this statistical analysis plan will be justified in the final report.

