5. Plug the MAXI into the oximeter and verify proper operation as described in the oximeter operator's manual.

Note: If the sensor does not track the pulse reliably, it may be incorrectly positioned—or the sensor site may be too thick, thin, or deeply pigmented, or otherwise deeply colored (for example, as a result of externally applied coloring such as nail polish, dye, or pigmented cream) to permit appropriate light transmission. If any of these situations occurs, reposition the sensor or choose an alternate sensor for use on a different site.

Model MAXN

- 1. Remove plastic backing from the MAX-N and locate transparent windows (a) on the adhesive side. Windows cover optical components. Note corresponding alignment marks (a) on the non-adhesive side and dashed line (b) midway between the marks. (1)
- 2. Orient the MAXN so the dashed line is on the lateral edge of the site.

Neonates: The preferred site is a foot. Alternatively, use a hand. The window next to the cable goes on the sole of the foot as shown. (2)

Adults: The preferred site is an index finger. Alternatively, other fingers may be used. The window next to the cable goes on the nail side, distal to the first joint. Do not place on a joint. Note that the cable must be positioned on the top of the hand. (3)

Note: When selecting a sensor site, priority should be given to an extremity free of an arterial catheter, blood pressure cuff, or intravascular infusion line.

- 3. Wrap the MAXN firmly, but not too tightly around the foot or finger. Windows must oppose each other.
- 4. Plug the MAXN into the oximeter and verify proper operation as described in the oximeter operator's manual.

Note: If the sensor does not track the pulse reliably, it may be incorrectly positioned—or the sensor site may be too thick, thin, or deeply pigmented, or otherwise deeply colored (for example, as a result of externally applied coloring such as nail polish, dye, or pigmented cream) to permit appropriate light transmission. If any of these situations occurs, reposition the sensor or choose an alternate sensor for use on a different site.

WARNINGS

Do not use the any oximetry sensors during MRI scanning. Conducted current may cause burns. Also, the sensors may affect the MRI image, and the MRI unit may affect the accuracy of oximetry measurements.

CAUTIONS

- 1. Do not use if package is damaged.
- 2. Failure to apply the sensor properly may cause incorrect measurements.

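### Skin tone is recorded for each infant but enters no planned accuracy analysis, so a pooled A_RMS within 3% could coexist with larger, unattributed error in darker-skinned infants

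*Combined protocol and SAP*

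**What the plan says.** Section 6.2.7 lists the extra CRF items: "Additional data recorded on the CRF will include the subject's gestational age, days of life, weight, length, reason for admission, and skin tone". Skin tone is scored on a named chart, "The skin tone will be evaluated using the Munsell System Soil Color Chart, Hue 7.5YR", with the value read at a specified body site. The result is an ordered score for each infant. No categories or cut-points are given.

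Section 8 does not mention skin tone. Section 8.3 pools the pairs apart from four exclusions for implausible or anomalous readings: "All data pairs will be included for analysis, unless at the time of data acquisition any one or more of the following is true". Section 8.4 calculates A_RMS, mean bias, SD_res, a Bland-Altman plot and an error plot for each sensor on those pooled pairs. It adds that "Between and within subject variance and upper and lower 95% limits of agreement will be presented" and that "Subject demographic data will be presented with summary statistics and site-level effects will be assessed as appropriate". Site is the only factor named for assessment. An A_RMS of at most 3% is expected of each sensor.

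Recruitment is a convenience sample (8.2), with no quota or minimum by skin tone. The appended MAXN instructions for use say that, when the pulse is not tracked reliably, "the sensor site may be too thick, thin, or deeply pigmented". The Masimo warnings list dyes, applied colouring, bilirubin, anaemia, perfusion and other causes of error. Skin pigmentation is not among them.

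**The concern.** The objective in section 3 is to validate accuracy, bias and precision in neonates. A root mean square over all pairs is a weighted average of squared error, so a minority of infants with larger error can be outweighed by the rest. The sponsor collects a graded skin-tone score for each infant and then gives it no role in any accuracy output.

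If error did vary with skin tone, the report could state that the sensor met the 3% figure in neonates with nothing linking the excess error to the infants concerned. A breakdown made later from the CRF would be unplanned, with the cut and the model chosen after the data were seen.

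**Working it through.** **The plan's own figure.** Section 8.1 takes 40 pairs (Bland-Altman) as the larger requirement and doubles it: 2 × 40 = 80 pairs per sensor. At most three pairs per infant gives 80/3 = 26.7, rounded up to 27, which matches "such that no subject contributes more than three data pairs for each of the two product sensors, for a minimum of 27 subjects". No subgroup size is stated. The component figures of 18 and 40 cannot be checked, because their inputs are not given.

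**Can pooling mask a difference?** It follows from equation 1.1 that, if a share f of pairs comes from darker-skinned infants,

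pooled A_RMS² = f × A_dark² + (1 − f) × A_other².

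The values of f and A_dark are assumptions throughout.

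- With f = 0.25, A_dark = 3.9 and A_other = 2.0: √(0.25 × 15.21 + 0.75 × 4.00) = √6.80 = 2.61, within 3%.
- Next, set A_other to the adult 70–100% figures in the instructions for use: 1.6 for Neo 2329 and 1.7 for MAXN. The largest A_dark that still pools to 3% is √[(9 − (1 − f) × A_other²)/f]. At f = 0.20 this is √(6.952/0.20) = 5.9 (Masimo) and √(6.688/0.20) = 5.8 (Nellcor).
- Masking has limits. At f = 0.30 and A_dark = 5.0 the pooled value is 3.05 (Masimo) or 3.09 (Nellcor), which exceeds 3%.

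**How precise would a descriptive look be?** Assume a between-infant SD (SD_b) of 1.0 to 1.5, a within-infant SD (SD_w) of 1.7 to 2.0, and three pairs per infant. The SD of an infant mean is √(SD_b² + SD_w²/3), which runs from √(1.00 + 0.963) = 1.40 to √(2.25 + 1.333) = 1.89. The 95% half-width for a difference in mean bias is t × that SD × √(1/n₁ + 1/n₂), with t ≈ 2.06:

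| Split (infants) | √(1/n₁ + 1/n₂) | Half-width (points) |
|---|---|---|
| 14:14 | 0.378 | 1.09–1.47 |
| 7:21 | 0.436 | 1.26–1.70 |
| 3:24 | 0.612 | 1.77–2.39 |
| 2:25 | 0.735 | 2.12–2.87 |

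The first two rows use 28 infants and the last two use 27. The enrolled mix is unknown. If 10% of the source population were darker-skinned, the binomial chance of two or fewer such infants among 27 is about 0.485.

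**Subgroup A_RMS is weaker still.** For an observed 3.9 in 7 infants (21 pairs), the chi-square 95% CI is 3.9 × √(df/χ²). This gives about 3.0 to 5.6 with 21 independent pairs (df = 21), and about 2.6 to 7.9 if each infant counts as one unit (df = 7).

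**The case against.** Several points on the other side are sound.

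- **No evidence of a skin-tone bias.** A reader might take the MAXN note as the sponsor's admission that SpO2 is biased in darker skin. It is not. The note concerns unreliable pulse tracking, gives externally applied colouring as its example of deep colour, and advises repositioning or another sensor. It covers only the Nellcor product. The 3.9 above is an assumption, more than twice the adult 1.6 and 1.7.
- **The plan is not wholly blind.** A reader might infer that skin tone is ignored altogether, or that a large difference would be invisible. Skin tone may be tabulated with the demographics. If the illustrated excess were all infant-level bias, it would be √(3.9² − 2.0²) = 3.35 points in 25% of infants. The between-infant SD would then rise from 1.0–1.5 to √(SD_b² + 0.25 × 0.75 × 3.35²) = 1.8–2.1, and between-subject variance is a planned output. What the plan lacks is attribution of that variation to skin tone.
- **Precision depends on the mix.** A reader might infer that 27 infants suffice to detect any difference that matters. The table shows that this holds only for favourable splits. It also concerns mean bias: excess scatter would not appear in a slope, although the plot could show it.
- **Other covariates.** Gestational age, days of life and weight are also recorded without a stated accuracy analysis, and the plan makes no subgroup claim. Whether the cited ISO standard or FDA guidance asks for a breakdown cannot be judged from these documents.

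These points limit how strongly the concern can be stated. They do not remove the gap between recording a graded score and planning no accuracy output that uses it. Section 8.4 already provides for site effects in the same small sample, so sample size alone does not justify the omission.

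**Conclusion.** The point holds in a limited form. Skin tone enters no planned accuracy analysis, and equation 1.1 allows a pooled A_RMS within 3% while error is larger in darker-skinned infants, without any planned output attributing the difference to skin tone. The size shown (2.61 pooled with a 25% subgroup at 3.9, or a 20% subgroup as high as 5.8 to 5.9 with adult-level error elsewhere) rests on assumed shares and subgroup errors. It establishes that masking is possible, not that it is likely. The half-widths rest on assumed SDs and an unknown skin-tone mix. The planned sample can support a descriptive look, but it was not sized to confirm or refute 3% in any skin-tone group.

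**What to change.** Add a paragraph to 8.4, per sensor and labelled descriptive:

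1. A plot of SpO2 minus SaO2 against Munsell value.
2. A mixed model of SpO2 minus SaO2 on Munsell value and SaO2 with a random infant effect, reporting the slope with its 95% CI.
3. The number of infants at each Munsell value, with the accuracy statement limited to the skin tones enrolled.
4. A_RMS and bias either side of a lighter/darker cut fixed before the data are seen, only if each group reaches a pre-stated minimum number of infants. Use subject-clustered CIs and make no pass/fail claim.

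State that the absence of a visible trend is not evidence of equal accuracy.

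The cost is a paragraph, one plot and one model per sensor, and a small table. No new data are needed. The downside is that intervals may be wide, and item 4 may not be reportable if few darker-skinned infants are enrolled.

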7 ADVERSE DEVICE EVENTS

7.1 Definition of Adverse Device Event (ADE)

The ADE is the adverse event (AE) related to the use of an investigational medical device resulting from insufficiencies or inadequacies in the IFU, the deployment, installation, the operation, or any malfunction of the investigational medical device or from error use.

7.2 Definition of Serious Adverse Device Event (SADE)

The SADE is the adverse device effect that has resulted in any of the consequences characteristic of a serious adverse event (SAE).

The FDA definition of SAE will be used in this study: An AE or suspected adverse reaction is considered "serious" if, in the view of either the PI or sponsor, it results in any of the following outcomes:

- Death
- A life-threatening adverse event
- Inpatient hospitalization or prolongation of existing hospitalization
- A persistent or significant incapacity or substantial disruption of the ability to conduct normal life functions or,
- A congenital anomaly/birth defect.

Important medical events that may not result in death, be life-threatening, or require hospitalization may be considered serious when, based upon appropriate medical judgment, they may jeopardize the subject's participation and may require medical or surgical intervention to prevent one of the outcomes listed in this definition. All SADEs will be reported to Medline, regardless of potential relationship to the investigational device. SADEs will be reported to the reviewing IRB as necessary according to their rules.

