4.2. End of Study Definition

A subject's participation in the study may end at several critical points:

• When the maximum number of blood draws, as per SOC (three), has been reached

- The maximum duration of sensor wear time has been reached, as per SOC or IFU, whichever occurs first.
- The PI or patient care team believes it is in the subject's best interest to discontinue in the study.
- Parent or legal guardian of the subject withdraws the subject from the study for any reason.

If the subject withdraws from the study, they will be replaced by another subject.

The study will be considered complete upon issuance of a Clinical Study Report that has been approved by the Clinical Affairs Director.

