7.8 Serious Adverse Device Event and Unanticipated Adverse Device Effect Reporting

The site PI shall complete a SAE Form provided by Medline Industries, LP and submit to the study sponsor, but in no event later than 48 hours after the investigator first learns of the effect. The site PI shall report the SADE to the reviewing IRB, if applicable, according to their reporting requirements. The study sponsor is responsible for conducting an evaluation of the SADE and shall report the results of such evaluation to the FDA and to all reviewing IRBs if applicable within 10 working days after the sponsor first receives notice of the effect. Thereafter, the sponsor shall submit such additional reports concerning the effect as FDA requests.

For questions regarding this process or the event, you may contact your Medline clinical designee or the Medline Director of Clinical Operations:

Name: [name] RN, BSN, CCRA [contact] E-mail: [contact]

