- 3. While the sensor is designed to reduce the effects of ambient light, excessive light may cause inaccurate measurements. In such cases, cover the sensor with opaque material.
- 4. Circulation distal to the sensor site should be checked routinely. The site must be inspected every 8 hours to ensure adhesion, skin integrity, and correct optical alignment. If skin integrity changes, move the sensor to another site.
- 5. Intravascular dyes or externally applied coloring such as nail polish, dye, or pigmented cream may lead to inaccurate measurements.
- 6. Motion may compromise performance. In such cases, try to keep the patient still, or change the sensor site to one with less motion.
- 7. Do not immerse in water or cleaning solutions. Do not sterilize. Immersion or sterilization could damage the sensor.
- 8. If the sensor is wrapped too tightly or supplemental tape is applied, venous pulsations may lead to inaccurate saturation measurements.
- 9. Do not alter or modify the sensor. Alterations or modifications may affect performance or accuracy.
- 10. The operator must verify the compatibility of the monitor, sensor, and cable before use, otherwise patient injury can result.
- 11. Misapplication of a pulse oximeter sensor with excessive pressure for prolonged periods can induce pressure injury.
- 12. For additional warnings, cautions or contraindications with Nellcor pulse oximeters, refer to the instrument operator's manual or contact the manufacturer of the instrument.

ACCURACY SPECIFICATIONS

The Medline ReNewal Reprocessed Nellcor OxiMax SpO₂ Sensors are indicated for the following conditions:

- SpO₂ range: 70 100%
- Pulse rate: 20 250 bpm

- Operating temperature: 5 40°C
- Storage temperature: -20 60°C
- Humidity: 15-95%

Table 1 provides the specifications of Medline ReNewal Reprocessed Nellcor OxiMax SpO₂ Sensors.

| Model Number | Sensor Type | Application Site | Saturation Accuracy (%) | Pulse Rate Accuracy (bpm) | Patient Weight (kg) |
|-----------------|--------------------------------------|---------------------|-------------------------------|---------------------------------|---------------------------|
| MAXA(L) | Adult Adhesive Sensor | Finger | ± 2 | ± 3 | > 30 |
| MAXP | Pediatric Adhesive Sensor | Finger | ±2 | ± 3 | 10 – 50 |
| MAXI | Infant Adhesive Sensor | Тое | ± 2 | ± 3 | 3 – 20 |
| MAXN | Neonatal/Adult Adhesive Sensor | Foot/Finger | ± 2 in adults | ± 3 | < 5 kg > 40 kg |

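### The important-medical-event clause in 7.2 asks whether study participation is jeopardized, not the infant's health or safety, so a device injury found as participation ends need not count as serious

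*Combined protocol and SAP*

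**What the plan says.** Section 7.2 names its source: "The FDA definition of SAE will be used in this study". It lists five outcomes that make an event serious: death, threat to life, hospitalization or its prolongation, lasting incapacity, and congenital anomaly. None of them depends on whether the subject is still in the study.

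The section then adds a route for important medical events that cause none of these. Such events "may be considered serious when, based upon appropriate medical judgment". Two conditions then apply together: the event may threaten the infant's "participation and may require medical or surgical intervention to prevent one of the outcomes listed in this definition".

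Section 4.2 gives the points at which participation may end. One is "When the maximum number of blood draws, as per SOC (three), has been reached"; another is the maximum sensor wear time under standard of care or the instructions for use (IFU). Section 1.1 puts subject duration at about 15 episodic minutes at the time of the draw, and allows the disconnected sensor to stay on for its maximum allowable duration. Under 6.2.6 the sensor is collected once participation is complete.

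Section 7.8 requires the site to send its serious-event form to the sponsor "in no event later than 48 hours after the investigator first learns of the effect". The sponsor must evaluate the event and report the result, where applicable, within 10 working days. Section 7.7 sends non-serious adverse device events to the sponsor for review and gives no time limit.

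**The concern.** An important-medical-event clause exists to catch harm that is averted by treatment and so never shows up as a listed outcome. Whether such harm is serious should not turn on whether data collection can continue.

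The distinction has practical weight here because participation is short and the harms named in the appendix arise under the sensor. The Nellcor IFU cautions: "Misapplication of a pulse oximeter sensor with excessive pressure for prolonged periods can induce pressure injury". The Masimo IFU warns of pressure necrosis and skin damage. Such an injury may first be seen when the sensor comes off.

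The clause also carries more load than it would in outpatients. Subjects are enrolled at neonatal intensive care centers, so most are already inpatients. For them the hospitalization criterion, "Inpatient hospitalization or prolongation of existing hospitalization", comes down largely to prolongation, which is hard to attribute to a skin injury in an infant whose stay has other causes.

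What is at stake is the SADE class and the two time limits attached to it.

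**Working it through.** No arithmetic applies: the point depends on no sample size, variance or event rate, and the plan gives no figure to reproduce. The check is a logical reading of 7.2 against the sections that define participation and the other reporting routes.

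**Step 1. Structure of the definition.** Let L = the event causes one of the five listed outcomes; P = it may jeopardize participation; I = it may require medical or surgical intervention to prevent a listed outcome. As written, an event can be serious if L, or if (P and I) in the assessor's medical judgment.

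| Case | L | I | P | Clause as written | With health or safety in place of participation |
|---|---|---|---|---|---|
| 1 | yes | any | any | serious through the list | serious through the list |
| 2 | no | no | any | not met | not met |
| 3 | no | yes | yes | can be serious | can be serious if health or safety may be jeopardized |
| 4 | no | yes | no | not met | can be serious if health or safety may be jeopardized |

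The gap is case 4 only.

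**Step 2. When can P be false while I is true?**
- *Participation over or ending.* By 4.2 it can stop at the third draw or at the wear limit. By 6.2.6 the sensor is collected after completion. The skin under it may therefore first be seen when no participation is left to jeopardize. Once participation is over, P is false however great the need for intervention; while it is ending, P is doubtful.
- *Participation continuing.* Section 6.2.6 lets the team move a sensor to another location. An injury at one site can need intervention without threatening further readings elsewhere.

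**Step 3. Do other routes catch case 4?**
- *Non-serious reporting (7.7).* Yes, the event reaches the sponsor, but no deadline is stated.
- *Unanticipated adverse device effect (7.3).* This definition does not mention participation. It needs a serious effect or problem, or a life-threatening one or a death, that was not previously identified or anticipated. Section 7.6 lists a reaction or irritation where the sensor was applied as expected, which makes this route uncertain for sensor-site injuries.
- *Scheduled assessment (1.2).* Adverse events are assessed at Day 0 and Day 1, and no later safety visit is scheduled.

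No other section rewrites the sentence in 7.2.

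**The case against.** Four objections have force.

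1. **The intervention condition already excludes ordinary lesions.** A reader might infer that any pressure injury needing treatment but not prolonging the stay escapes because of the participation wording. The text does not support that. The intervention must be needed to prevent a listed outcome, so a routinely treated sore fails the clause under either wording (case 2). Section 7.4 also has a Moderate grade for events that need treatment without extended hospitalization. This stands, and it makes the affected set small.

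2. **The clause is permissive.** It says such events may be considered serious on medical judgment, so an assessor could still reach the right class. This stands: escape is possible, not certain. But the sentence directs that judgment to participation.

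3. **Affected events are not hidden.** A reader might infer that they go unreported. Section 7.7 still sends them to the sponsor, and 7.2 lets either the investigator or the sponsor judge whether a listed outcome has occurred. What is lost is the SADE class and its time limits.

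4. **Injuries can be found during wear.** The sensor may stay on well beyond 15 minutes, both IFUs call for site inspection every eight hours, and 4.2 allows discontinuation in the subject's best interest. An injury found then can threaten participation and meet the clause. This narrows the gap but leaves injuries found at or after the end of participation, and those that do not threaten continuation.

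Two further inferences are tempting. One is that the two conditions should be alternatives, with *or* in place of *and*. The argument shows only that the wrong thing is said to be jeopardized, and nothing in the documents supports changing the conjunction. The other is that the sentence departs from the FDA definition. That text is not reproduced in the protocol, so a difference cannot be confirmed, and the point does not rest on one.

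**Conclusion.** The point holds as a defect of wording in a safety definition. Under 7.2 as written, a device injury that needs intervention to prevent a listed outcome need not be classed as serious if it is found at or after the end of participation, or if it does not threaten continuation. It could then follow 7.7, with no stated deadline, and not 7.8.

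The number of affected events cannot be computed from the documents and is probably small, since an event must meet the intervention condition, cause none of the five outcomes and leave participation untouched. The conclusion assumes that assessors apply the sentence as written and that participation means participation in this study. No endpoint, sample size or analysis is affected.

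**What to change.** In 7.2, in the sentence on important medical events, replace the subject's *participation* with the subject's *health or safety*. Keep the rest of the sentence, including *and*. Have the sponsor check the amended sentence against the FDA definition that the section says it adopts.

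The cost is a one-line amendment and possibly a few more serious reports.
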